4. STUDY DESIGN

4.1. Overview of Study Design

This is a phase 2 study designed to examine the bone anabolic effect of the next generation proteasome inhibitor, ixazomib, in relapsed/refractory myeloma patients. Treatment consists of ixazomib 4 mg on days 1, 8, 15, 22 of a 28-day cycle, for a maximum of 6 cycles).

General eligibility criteria may be assessed prior to the formal Screening period if it is part of standard clinical practice. However, per the Schedule of Events, formal screening will occur during the Screening period, which may last for up to 35 days prior to initiating study treatment. Determination of relapsed/refractory disease as an entry criterion may be based on patient data obtained during or following the patient's most recent prior antineoplastic therapy.

Study drug (ixazomib 4.0 mg) will be given on Days 1, 8, 15, 22 of a 28- day cycle for a maximum of 6 cycles. Dose modifications may be made based on toxicities during treatment. Patients will be discontinued from the study for progressive disease or unacceptable toxicity.

Treatment periods will be defined as 28-day cycles. Patients will be seen once per treatment cycle (Day 1) during their participation in the active treatment of the study. More frequent follow-up would be only as clinically indicated at the discretion of the treating physician.

Patients will be assessed for disease response and progression. Response will be assessed according to the International Myeloma Working Group (IMWG) criteria (see APPENDIX A) for all patients every 4 weeks for a maximum of 6 cycles (unless disease progression or unacceptable toxicity).

ECOG performance score (APPENDIX B), adverse events (AEs), laboratory values, and vital sign measurements will be collected and assessed throughout the study. Toxicity will be evaluated according to National Cancer Institute Common Terminology Criteria for Adverse Events (NCI CTCAE), version 4.03, effective date 14 June 2010.

Patients will attend an End of Treatment (EOT) visit after completion of their 6 cycles (or at study discontinuation due to progressive disease, unacceptable toxicity, or other reason) and will continue to be followed for survival.

4.2. Number of Patients

20 patients, male or female, 18 years of age or older, will be enrolled in this study.

4.3. Duration of Study

The duration of this study will be approximately 26 months, including 20 months for enrollment of subjects and approximately 6 months of treatment from the last patient enrolled.

Patients may remain on treatment for a maximum of 6 cycles, unless the occurrence of progressive disease or unacceptable toxicity (or other reason). Patients will continue to be followed for survival.

5. STUDY POPULATION

5.1. Inclusion Criteria

Each patient must meet all of the following inclusion criteria to be enrolled in the study:

- Male or female patients 18 years or older.
- Voluntary written consent must be given before performance of any study related procedure not part of standard medical care, with the understanding that consent may be withdrawn by the patient at any time without prejudice to future medical care.

- Female patients who:
 - Are postmenopausal for at least 1 year before the screening visit, OR
 - Are surgically sterile, OR
 - If they are of childbearing potential, agree to practice 2 effective methods of contraception, at the same time, from the time of signing the informed consent form through 90 days after the last dose of study drug, AND
 - Agree to practice true abstinence when this is in line with the preferred and usual lifestyle of the subject. (Periodic abstinence [eg, calendar, ovulation, symptothermal, post-ovulation methods] and withdrawal are not acceptable methods of contraception.)
- Male patients, even if surgically sterilized (ie, status post-vasectomy), must agree to one of the following:
 - Agree to practice effective barrier contraception during the entire study treatment period and through 90 days after the last dose of study drug, OR
 - Agree to practice true abstinence when this is in line with the preferred and usual lifestyle of the subject. (Periodic abstinence (eg, calendar, ovulation, symptothermal, post-ovulation methods] and withdrawal are not acceptable methods of contraception.)
- Patients must have a diagnosis of relapsed/refractory multiple myeloma and must have received at least one line of prior therapy.
- Eastern Cooperative Oncology Group (ECOG) performance status and/or other performance status 0, 1, or 2.
- Patients must meet the following clinical laboratory criteria:
 - Absolute neutrophil count (ANC) ≥ 1,000/mm3 and platelet count ≥ 75,000/mm3. Platelet transfusions to help patients meet eligibility criteria are not allowed within 3 days before study enrollment.
 - Total bilirubin $\leq 1.5 \times$ the upper limit of the normal range (ULN).
 - Alanine aminotransferase (ALT) and aspartate aminotransferase (AST) \leq 3 × ULN.
 - Calculated creatinine clearance \geq 30 mL/min.

5.2. Exclusion Criteria

Patients meeting any of the following exclusion criteria are not to be enrolled in the study:

- Patients that have not been previously treated with a multi-drug regimen including a proteasome inhibitor, immunomodulatory drug, and corticosteroid.
- Female patients who are lactating or have a positive serum pregnancy test during the screening period.

- Failure to have fully recovered (ie, ≤ Grade 1 toxicity) from the reversible effects of prior chemotherapy.
- Major surgery within 14 days before enrollment.
- Radiotherapy within 14 days before enrollment. If the involved field is small (in the opinion of the enrolling investigator), 7 days will be considered a sufficient interval between treatment and administration of the ixazomib.
- Patients who have non-myeloma related bone disease that will interfere with the interpretation of the bone-related blood and radiology assessments, including Paget's disease, Rickets, Osteomalacia, and any other metastatic bone cancer.
- History of myeloma-related central nervous system involvement.
- Infection requiring systemic antibiotic therapy or other serious infection within 14 days before study enrollment.
- Evidence of current uncontrolled cardiovascular conditions, including uncontrolled hypertension, uncontrolled cardiac arrhythmias, symptomatic congestive heart failure, unstable angina, or myocardial infarction within the past 6 months.
- Systemic treatment, within 14 days before the first dose of ixazomib, with strong inhibitors of CYP1A2 (fluvoxamine, enoxacin, ciprofloxacin), strong inhibitors of CYP3A (clarithromycin, telithromycin, itraconazole, voriconazole, ketoconazole, nefazodone, posaconazole) or strong CYP3A inducers (rifampin, rifapentine, rifabutin, carbamazepine, phenytoin, phenobarbital), or use of Ginkgo biloba or St. John's wort.
- Ongoing or active systemic infection, known active hepatitis B or C virus infection, or known human immunodeficiency virus (HIV) positive.
- Any serious medical or psychiatric illness that could, in the investigator's opinion, potentially interfere with the completion of treatment according to this protocol.
- Known allergy to any of the study medications, their analogues, or excipients in the various formulations of any agent.
- Known GI disease or history of GI procedure that could interfere with the oral absorption or tolerance of ixazomib including difficulty swallowing.
- Diagnosed or treated for another malignancy within 2 years before study enrollment or previously diagnosed with another malignancy and have any evidence of residual disease. Patients with non-melanoma skin cancer or carcinoma in situ of any type are not excluded if they have undergone complete resection.
- Patient has ≥ Grade 3 peripheral neuropathy, or Grade 2 with pain on clinical examination during the screening period.
- Participation in other clinical trials, including those with other investigational agents not included in this trial, within 21 days of the start of this trial and throughout the duration of this trial.

 Patients who have taken bisphosphonate or RANK Ligand Inhibitor within 3 weeks from screening.

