3. STUDY ENDPOINTS

3.1. Primary Endpoint

The primary endpoint of this study is change in serum osteocalcin from baseline to study exit.

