8.2.3.5. Excluded Concomitant Medications and Procedures

The following medications and procedures are prohibited during the study:

- Systemic treatment with any of the following metabolizing enzyme inhibitors is not permitted during this study. A DDI with a strong inhibitor would increase MLN2238 exposure.
 - Strong inhibitors of CYP1A2: fluvoxamine, enoxacin, ciprofloxacin
 - Strong inhibitors of CYP3A: clarithromycin, telithromycin, itraconazole, voriconazole, ketoconazole, nefazodone, and posaconazole
- Systemic treatment with any of the following metabolizing enzyme inducers should be avoided unless there is no appropriate alternative medication for the patient to use. A DDI with a strong inducer would decrease MLN2238 exposure.
 - Strong CYP3A inducers: rifampin, rifapentine, rifabutin, carbamazepine, phenytoin, and phenobarbital
 - The dietary supplements St John's wort and Ginkgo biloba are not permitted.
- Additional treatment or procedures prohibited during the study:
 - Adjuvant hormone therapy for breast or prostate cancer.
 - Bisphosphonates: Concomitant treatment with bisphosphonates will not be permitted.
 - Any antineoplastic treatment with activity against MM except for drugs in this treatment regimen.
 - Radiation therapy (the requirement for local radiation therapy generally indicates disease progression).
 - Platelet transfusions to help patients meet eligibility criteria are not allowed within 3 days before study drug dosing.

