8.2.3.6. Permitted Concomitant Medications and Procedures

The following medications and procedures are permitted during the study:

- Antiemetics, including 5-HT3 serotonin receptor antagonists, may be used at the discretion of the investigator.
- Loperamide or other antidiarrheal should be used for symptomatic diarrhea at discretion of the investigator. The dose and regimen will be according to institutional guidelines. IVF should be given to prevent volume depletion.
- Growth factors (eg, granulocyte colony stimulating factor [G-CSF], granulocyte macrophage-colony stimulating factor [GM-CSF], recombinant erythropoietin) are permitted. Their use should follow published guidelines and/or institutional practice; however, alternative usage may be reviewed with the Millennium Clinical or Medical

Representative . Erythropoietin will be allowed in this study. Their use should follow published guidelines and/or institutional practice.

- Patients should be transfused with red cells and platelets as clinically indicated (except as noted in 8.2.4) and according to institutional guidelines.
- Antiviral therapy such as acyclovir may be administered if medically appropriate.
- Patients who experience worsening neuropathy from baseline may be observed for recovery, and have dose reductions/delays as indicated in the protocol, and any supportive therapy or intervention may be initiated as appropriate at the discretion of the investigator.
- Supportive measures consistent with optimal patient care may be given throughout the study.

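### RANK-ligand inhibitors are excluded at entry but not barred on study, so one may be started between the two osteocalcin samples of the uncontrolled primary endpoint

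*Combined protocol and SAP*

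**What the plan says.** Section 5.2 (Exclusion Criteria) keeps out "Patients who have taken bisphosphonate or RANK Ligand Inhibitor within 3 weeks from screening". The same list excludes non-myeloma bone disease that "will interfere with the interpretation of the bone-related blood and radiology assessments".

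For the treatment period, Section 8.2.3.5 says "Bisphosphonates: Concomitant treatment with bisphosphonates will not be permitted". That is its only entry on bone-modifying agents. Its other entries cover CYP inhibitors and inducers, two supplements, hormone therapy, anti-myeloma drugs, radiation and platelet transfusions. Section 8.2.3.6 adds that "Supportive measures consistent with optimal patient care may be given throughout the study".

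Section 3.1 states: "The primary endpoint of this study is change in serum osteocalcin from baseline to study exit". Section 9.1 describes a single-arm study of 20 patients, tested with a signed-rank test (or a paired t-test if normality holds) at a one-sided 0.05 level. It has no rule for a bone-active drug started during treatment.

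**The concern.** The protocol treats recent use of either bone-agent class as disqualifying, but carries only one of the two into the treatment period. Treatment can last 6 × 28 = 168 days without delays. Section 1.1.2 says bone disease affects most patients and brings fractures and cord compression, so a clinician may well want bone protection. With bisphosphonates barred, the other class named in 5.2 remains open.

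The primary endpoint is a within-patient change with no comparator. If a RANK-ligand inhibitor starts between the two samples, that patient's change mixes two drugs and nothing in the design separates them. BALP, NTX and the Dexascan T scores, all secondary endpoints, cover the same window.

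**Working it through.** **1. Entry rules against on-study rules.** Section 5.2 names seven drug or supplement groups by recent use:

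| Group named in 5.2 | On-study rule in 8.2.3.5 |
|---|---|
| Strong CYP1A2 inhibitors ("Systemic treatment, within 14 days before the first dose of ixazomib, with strong inhibitors of CYP1A2") | Barred: "Systemic treatment with any of the following metabolizing enzyme inhibitors is not permitted during this study" |
| Strong CYP3A inhibitors | Barred by the same rule |
| Strong CYP3A inducers | "should be avoided unless there is no appropriate alternative medication for the patient to use" |
| Ginkgo biloba | Barred |
| St. John's wort | Barred |
| Bisphosphonates | Barred |
| RANK-ligand inhibitors | None |

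Six of the seven have an on-study rule. The bar on antineoplastic drugs active against myeloma does not name RANK-ligand inhibitors. The text does not show whether the omission is deliberate.

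**2. The plan's own figure.** Inputs from Section 9.1: osteocalcin 7.46 ng/ml (SD 12.65) before and 19 ng/ml (SD 18.6) after, correlation 0.5, n = 20, one-sided 0.05, stated power 88%.

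- Planned change: 19 − 7.46 = 11.54 ng/ml.
- SD of change: √(12.65² + 18.6² − 2 × 0.5 × 12.65 × 18.6) = 16.45.
- Standardised effect: 11.54 / 16.45 = 0.701.
- Noncentral t with effective n = 20 × 0.864 = 17.28 (0.864 is the minimum asymptotic relative efficiency): power 87.4%, close to the stated 88%.
- Simulating the signed-rank test on normal differences gives 90%, which is the base used in step 4.

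**3. Upper bound with no assumed effect size.** For n = 20 the exact one-sided test rejects when W⁺ ≥ 150 (level 0.0487). Suppose ixazomib does nothing and k starters have arbitrarily large rises. They take the top k ranks, all positive, so the rejection probability is that of W⁺ on the other 20 − k patients reaching 150 minus the sum of those ranks.

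| k | Calculation | Chance of a positive result |
|---|---|---|
| 0 | P(W₂₀ ≥ 150) | 4.9% |
| 1 | P(W₁₉ ≥ 150 − 20 = 130) | 8.4% |
| 2 | P(W₁₈ ≥ 150 − 39 = 111) | 14.2% |
| 4 | P(W₁₆ ≥ 150 − 74 = 76) | 35.3% |

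**4. Assumed range.** The documents give no effect size, so I assume a shift in each starter of half (5.77) or all (11.54 ng/ml) of the planned change, with normal differences and SD 16.45. Each pair below is for 5.77 / 11.54.

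| Starters | False-positive rate, upward shift, no ixazomib effect | Power, downward shift, planned effect real |
|---|---|---|
| 0 | 4.9% | 90% |
| 1 | 5.6% / 6.3% | 88.7% / 87.1% |
| 2 | 6.5% / 8.1% | 87.2% / 83.3% |
| 4 | 8.4% / 12.7% | 83.7% / 74.0% |

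Steps 3 and 4 apply to the signed-rank test; the paired t-test alternative was not examined.

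**The case against.** **No mechanism is documented.** No section says how this class changes osteocalcin, and the exclusion in 5.2 gives no reason. The wording about interference with bone assessments belongs to a different item in the list. This stands: an effect on osteocalcin is a reasonable inference, but the documents do not establish it, and no direction can be claimed.

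**The likely effect is small.** One starter moves the false-positive rate only to 5.6–6.3%, or power to 87–89%. The larger figures need four of 20 patients shifted the same way. This stands too, and it limits the severity.

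**The carry-over pattern is imperfect.** Other investigational agents are also absent from 8.2.3.5, and CYP3A inducers are only discouraged. However, 5.2 itself extends the ban on other trials, including their agents, through the study. RANK-ligand inhibitors remain the only group without any on-study rule.

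**Existing rules already help.** New or growing bone lesions, and hypercalcemia due solely to myeloma, count as progression (Appendix A). Progression ends participation (4.1), and the End of Treatment procedures are done at withdrawal (8.2.6). Some likely starters would therefore give their exit sample first. Elective use is not covered.

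**A ban has a clinical cost.** It would remove both named bone-agent classes for up to 168 days, and a clinical-need provision would let through some of the likeliest uses. That is a genuine trade-off, so the recording and analysis steps matter as much as the ban.

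**Conclusion.** The gap is real. Followed exactly, the plan lets a patient start a RANK-ligand inhibitor between the two samples that define an uncontrolled primary endpoint, and gives no rule for analysing that patient.

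Severity is minor to moderate. A few starters would be unlikely to create a positive result alone: with one to four starters and shifts of half to all of the planned change, the false-positive rate is 5.6% to 12.7% if upward, and power is 89% to 74% if downward. The number of starters and the size and direction of the shift are assumptions. The exact bounds need no effect size, but they assume every starter shifts upward without limit. The change is worth making because it is nearly free and touches the primary endpoint.

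**What to change.** 1. Extend the bisphosphonate line in 8.2.3.5, for example: *Neither bisphosphonates nor RANK-ligand inhibitors may be given during study treatment; if clinical need arises, treat the patient and record the use.* If a ban is judged too strict, the wording already used there for CYP3A inducers is a softer option.
2. Record the start date of any bone-active agent in the treatment history already taken at every visit (6.1 and Section 7, footnote 1).
3. Keep baseline to exit as the primary analysis. If anyone starts such an agent, add a sensitivity analysis using that patient's last osteocalcin before the start. This value reflects shorter ixazomib exposure, so it supplements the primary result and does not replace it. A patient who starts before the Cycle 2 Day 1 sample has no on-treatment value before the start and should be listed separately.

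**Cost:** one amendment line, one recorded date, and a small analysis only if a start occurs. No visits or blood draws are added, because Section 6.2 already schedules osteocalcin at baseline, day 1 of cycles 2–6 and end of study. The downside is restricted access to bone protection for up to six cycles, hence the clinical-need provision. If the omission was deliberate, steps 2 and 3 are still worth adopting.

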6. TREATMENT PLAN

All baseline assessments, labs, and bone marrow biopsies are to be completed within 35 days of enrollment. Radiological studies are to be completed within 60 days prior to enrollment.

Study drug (ixazomib 4.0 mg) will be given on Days 1, 8, 15, 22 of a 28- day cycle for a maximum of 6 cycles.

For a new cycle of treatment to begin, the patient must meet the following criteria:

- ANC must be $\geq 1,000/\text{mm}^3$.
- Platelet count must be \geq 75,000/mm³.
- All other non-hematologic toxicities should, at the investigator's discretion, generally be recovered to patient's baseline condition or Grade 1 or lower.

Dose modifications may be made based on toxicities during treatment described in detail in section 8.2.3. Treatment periods will be defined as 28-day cycles. Patients will be seen in clinic once per treatment cycle (Day 1) during their participation in the active treatment of the study. More frequent follow-up would be only as clinically indicated at the discretion of the treating physician.

Patients will be assessed for disease response and progression. Response will be assessed according to the IMWG criteria (see APPENDIX A) for all patients every 4 weeks for a maximum of 6 cycles (unless disease progression or unacceptable toxicity).

Patients will attend an End of Treatment (EOT) visit after completion of their 6 cycles (or at study discontinuation due to progressive disease, unacceptable toxicity, or other reason) and will continue to be followed for survival. Follow-up for survival after end of treatment will be limited to contact via telephone approximately annually to verify the patient's disposition. Verification of the patient's disposition may be performed by medical record review if the patient was seen in clinic at UAMS within 3 months of the scheduled follow-up interval.

6.1. Physical assessments

Physical Assessments include History and Physical (H&P), which includes a detailed medical and treatment history, vital signs, weight, height, and BSA, and performance evaluation (ECOG) as seen in Appendix B. H&P and performance evaluation will be performed at all visits. Toxicities will be evaluated according to National Cancer Institute Common Terminology Criteria for Adverse Events (NCI CTCAE), version 4.0, effective date 14 June 2010 starting with cycle 1.

6.2. Laboratory tests

Laboratory tests (CBC with differential, BMP, LFTs, Uric Acid, Albumin, CRP, Pregnancy Test (WOCBP)), bone marker tests (BALP, Osteocalcin, NTX, Vitamin D 25), and myeloma lab tests (Serum Protein Electrophoresis, Serum Quantitative Immunoglobulins, Serum Free Light Chains, Serum IFE and/or Urine Beta-2-Microglobulin) will be performed at baseline, on day 1 of cycles 2-6, and at end of study. BNP and TSH will be performed at baseline and end of study only.

6.3. Bone Marrow Tests

Bone marrow aspirate and biopsies will be performed at baseline and at the end of study for immunohistochemistry, cytogenetics, and flow cytometry.

Bone marrow aspirates and biopsies for gene expression profiling (GEP) are optional and will be performed in subjects providing informed consent. Based on the requirement of obtaining at least 3 million plasma cells, approximately 50 ccs of bone marrow aspirate will be collected in a EDTA syringe and sent to the Myeloma Institute Research lab for gene array studies. If there are insufficient plasma cells in the sample to perform gene array, an additional bone marrow pull and bone marrow biopsy may be requested. The sample should be clearly labeled "for separation for GEP for UARK 2014-14".

6.4. Radio-Imaging

The bone densitometry scan (Dexascan) and skeletal survey will be performed at baseline and at end of study.

7. SCHEDULE OF EVALUATIONS

All baseline assessments, labs, and bone marrow biopsies are to be completed within 35 days of enrollment. Radiological studies are to be completed within 60 days prior to enrollment.

	Screening/Baseline	Cycles 1-6	End of Treatment
P	HYSICAL ASSESSMENTS		•
H&P ¹	Х	Х	Х
Performance Evaluation (ECOG)	Х	Х	Х
Toxicity Evaluation		Х	Х
	LABORATORY		
CBC with differential	Х	Х	Х
Basic Metabolic Panel (BMP), Liver Function Tests (LFTs), Uric Acid, Albumin, and CRP ²	x	Х	x
BNP ³	Х		Х
Pregnancy Test ⁴ (WOCBPonly)	Х	Х	Х
TSH	Х		Х
BALP, Osteocalcin, NTX	Х	Х	Х
Vitamin D 25	Х	Х	Х
Serum Protein Electrophoresis	Х	Х	Х
Serum Quantitative Immunoglobulins	Х	Х	Х
24 hour urine for total protein, & electrophoresis and calcium	X	Х	х
Serum IFE and/or Urine Beta-2-Microglobulin ⁶	x	Х	х
Serum Free Light Chains	Х	Х	Х
	BONE MARROW		
Bone Marrow Aspirate & Biopsy and Gene Expression Profiling ⁵	X		х
	RADIO-IMAGING		
Bone Densitometry (Dexascan)	Х		Х
Skeletal Survey	Х		Х
BANK	ING FOR FUTURE RESEAR	СН	
Blood and/or bone marrow ⁷		Х	

1 History and Physical (H&P) includes a detailed medical and treatment history, vital signs, weight, height, and BSA.

2 BMP includes Na, K, CI, CO2, BUN, Creatinine, Ca, glucose; LFTs include bilirubin total and direct, SGOT, SGPT, Alkaline phosphatase,

albumin, total protein, and LDH

3 BNP = B-type natriuretic peptide

4 Required while receiving study drug for WOCBP (women of childbearing potential) only

5 BM Aspirate & Biopsy for immunohistochemistry, cytogenetics, and flow cytometry. GEP optional.

6 Upon disappearance of the Urine M and as clinically indicated.

7 Optional blood and/or bone marrow specimens may be collected and stored for future research at any time that sample collection is already required for other tests

